#### 5. Pre-specified post-hoc analyses:

- 5.1. The same models described in the analysis of primary objective 1.1 will be performed for the outcome.
- 5.2. The same models described in the analysis of exploratory objective 3.2 will be completed for each of the different outcomes.

Analysis population: The intention to treat population will be used for all analyses.

*Hypothesis testing:* For hypothesis testing, a 5% significance level will be used (two-sided). No interim analyses will be performed. For secondary objectives, nominal p-values will be reported.

*General model assumptions and model diagnostic procedures:* For the linear mixed-effects models with visit and treatment-by-visit interaction as covariates, a participant-level random intercept will be included. Restricted-maximum-likelihood will be used for estimation and the missing-at-random framework will be assumed. Plots of marginal and conditional residuals will be used for model diagnostics and assessment. Similar diagnostic procedures will be used for the linear regression models.

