5.3 Sample Size

The sample size is based on the primary endpoint of blood pressure. Currently, there is only one publication from our group with information available on the effect of SGLT2i on blood pressure reduction in KTR with diabetes. In this observational study of 10 KTR and simultaneous pancreas-kidney transplant recipients treated with canagliflozin, we reported a SBP decrease of $6.5 \pm 10 \text{ mmHg}^{63}$. Given the small sample size in our observational study, we believe the standard deviation would be smaller in a larger cohort. Blood pressure reduction with SGLT2 inhibition appear to be similar between patients with and without diabetes in non-transplant studies. We, therefore, estimated the sample size based on a SBP change of 6.5 mmHg with a standard deviation of 8 mmHg. Under the hypothesis that SGLT2i decreases SBP by $6.5 \pm 8 \text{ mmHg}$ compared to placebo with a two-sided alpha of 0.05 and 80% power, we calculate a sample size of n=48, with 24 randomized to dapagliflozin and 24 randomized to placebo. Assuming a 10% attrition rate, the final sample size required is 52 participants. This sample size is similar to those successfully used in previous studies⁷¹, and sufficient to measure secondary renal endpoints related to renal hemodynamic function⁷¹, natriuresis and arterial stiffness⁷²⁻⁷⁴. Based on previous studies, we anticipate an even sex distribution in each group.

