7.3 Summary of findings from clinical studies

SGLT2 is the predominant transporter responsible for reabsorption of glucose from the glomerular filtrate back into the circulation. Despite the presence of hyperglycaemia in type 2 diabetes, reabsorption of filtered glucose continues. Dapagliflozin improves both fasting and post-prandial plasma glucose levels by reducing renal glucose reabsorption leading to urinary glucose excretion. This glucose excretion (glycosuric effect) is observed after the first dose, is continuous over the 24-hour dosing interval and is sustained for the duration of treatment. The amount of glucose removed by the kidney through this mechanism is dependent upon the blood glucose concentration and GFR. In patients with low plasma glucose or low eGFR dapagliflozin's efficacy to lower HbA1c is low and so the risk of hypoglycemia is low as well. Effects on blood pressure, body mass index, albuminuria, hematocrit appear to be independent of GFR.

Dapagliflozin does not impair normal endogenous glucose production in response to hypoglycaemia. Dapagliflozin acts independently of insulin secretion and insulin action rendering the risk of hypoglycemia low. Increases in the amount of glucose excreted in the urine were observed in healthy subjects and in subjects with type 2 diabetes mellitus following the administration of dapagliflozin. Approximately 70 g of glucose was excreted in the urine per day (corresponding to 280 kcal/day) at a dapagliflozin dose of 10 mg/day in subjects with type 2 diabetes for 12 weeks. Evidence of sustained glucose excretion was seen in subjects with type 2 diabetes given dapagliflozin 10 mg/day for up to 2 years.

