# 1. Analysis for the primary objective:

- 1.1. To assess dapagliflozin-related acute and chronic changes in the primary outcome of seated systolic blood pressure compared to placebo, linear mixed-effects models will be used. Two separate models will be fit. For acute change, the vector of outcomes will include the baseline and 1-week values (i.e. Visit 3 and Visit 4 values). For chronic changes, the vector of outcomes will include the baseline and 12-week values (i.e. Visit 3 and Visit 9 values). The covariates will include the visit and treatment-by-visit interaction; due to randomization, a covariate for the main effect of treatment will not be included. The treatment-by-time coefficient, its 95% confidence interval, and its p-value will be used to assess the effect of treatment.
- 1.2. We will repeat this analysis with:
  - a. Seated diastolic blood pressure as an outcome
  - b. Seated mean arterial pressure as an outcome

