# 2. Analysis for secondary objective:

- 2.1. The numbers of hypoglycemic episodes, acute rejection episodes, volume depletion, UTI or genital infection, acute kidney injury, ketoacidosis and serious adverse events will be reported for both the placebo group and dapagliflozin group. No statistical comparisons will be performed.
- 2.2. 2.10. The same models described in the analysis of primary objective 1.1 will be completed for each of the different outcomes.

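### For outcomes analysed with SAP model 1.1, a random intercept alone implies equal variance at baseline and follow-up, so the treatment effect's standard error is wrong if spread changes

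*SAP*

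**What the plan says.** SAP analysis 1.1 fits two separate linear mixed models for seated systolic pressure: Visit 3 with Visit 4 (acute) and Visit 3 with Visit 9 (chronic). "The covariates will include the visit and treatment-by-visit interaction"; the treatment main effect is left out because of randomisation. The treatment-by-time coefficient, its 95% interval and its p-value carry the conclusion.

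The closing paragraph on model assumptions adds that "a participant-level random intercept will be included", that REML is used and data are assumed missing at random, and that marginal and conditional residuals will be plotted. It names no residual structure, visit-specific variance, robust standard error or degrees-of-freedom method.

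For the secondary objectives from 2.2 on, "The same models described in the analysis of primary objective 1.1 will be completed for each of the different outcomes". Diastolic and mean arterial pressure (1.2), the blood and urine chemistry of 3.8, which includes 24-hour urine glucose, and urine adenosine (5.1) use the same model. Estimated plasma volume (3.1), the association analyses 3.2-3.7 and the safety counts (2.1) do not.

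**The concern.** With two visits, a random intercept plus one residual variance is compound symmetry: a single variance for both visits and both arms. Because baseline means are constrained equal, the treatment effect is a follow-up contrast adjusted for baseline, and its true variance depends on the follow-up variance. The model puts the average of baseline and follow-up variance in its place. Type I error and interval coverage then depend on an assumption that the design does not need.

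The SAP's combination of choices creates this. Had a treatment main effect been included, then with complete data the model would reduce to a comparison of change scores, whose variance is estimated directly.

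**Working it through.** **1. The plan's own figure.** Protocol 5.3 assumes an "SBP change of 6.5 mmHg with a standard deviation of 8 mmHg", "with a two-sided alpha of 0.05 and 80% power". Per arm, n = 2 x (1.960 + 0.842)^2 x 8^2 / 6.5^2 = 23.8, so 24. This agrees with "with 24 randomized to dapagliflozin and 24 randomized to placebo", and power at 24 per arm is 80.4%. The checks below use 24 per arm. The 8 mmHg is an SD of change; it does not determine the baseline SD, the follow-up SD or their correlation.

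**2. Formula.** Let v0 and v1 be the baseline and follow-up variances, c their covariance and vbar = (v0 + v1)/2. Under compound symmetry:

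- The estimate is the follow-up difference minus r times the baseline difference, with r = c/vbar.
- The model's variance is (2/n) x vbar x (1 - r^2).
- The true variance is (2/n) x (v1 - 2rc + r^2 v0). Putting c = r x vbar gives (2/n) x v1 x (1 - r^2).

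With k = follow-up SD / baseline SD, model SE / true SE = sqrt(vbar/v1) = sqrt((1 + k^2)/(2k^2)), whatever the correlation. Large-sample type I error is 2 x (1 - Phi(1.96 x ratio)). At k = 1.25 the ratio is sqrt(2.5625/3.125) = 0.906, and 1.96 x 0.906 = 1.775 gives 7.6%.

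**3. Range over k.** The values of k are assumptions. The simulations use 24 per arm, complete normal data, assumed correlations of 0.4-0.7 and a t reference.

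| k | Model SE / true SE | Type I, formula | Type I, simulated |
|---|---|---|---|
| 0.8 | 1.132 | 2.7% | 2.5-3.7% |
| 1.0 | 1.000 | 5.0% | 5.0-5.5% |
| 1.1 | 0.956 | 6.1% | 6.1-6.3% |
| 1.17 (SD 12 to 14) | 0.931 | 6.8% | 6.7-7.3% |
| 1.25 (SD 12 to 15) | 0.906 | 7.6% | 7.4-8.3% |
| 1.5 | 0.850 | 9.6% | 8.8% |

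The treatment estimate showed no bias in these runs.

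**4. Spread rising on drug only.** With correlation 0.5, simulated type I error is 6.5% if the drug-arm SD rises by a factor of 1.25, and 10.8% if it doubles.

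**5. 24-hour urine glucose.** Protocol 7.3 reports, for type 2 diabetes on 10 mg/day: "Approximately 70 g of glucose was excreted in the urine per day". It also says that excretion depends on blood glucose and GFR. This trial mixes participants with and without diabetes and admits eGFR from 30 upward. The documents give no spread, so take an SD of 2-5 everywhere except 15-25 on drug at follow-up. The follow-up variance is then averaged over the arms:

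- SDs 5 and 15: v1 = (25 + 225)/2 = 125, vbar = (25 + 125)/2 = 75, ratio sqrt(75/125) = 0.77.
- SDs 2 and 25: v1 = (4 + 625)/2 = 314.5, vbar = (4 + 314.5)/2 = 159.25, ratio 0.71.

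Simulated coverage of the nominal 95% interval is 82-86%, against 94-95% for a baseline-adjusted analysis.

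**6. The alternative.** Baseline-adjusted ANCOVA rejected in about 4-6% of null trials across these settings. When only the drug-arm SD rose from 3 to 20, it rejected 5.3%, against 15.7% for the SAP model.

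**The case against.** The strongest reply is that unequal spread is not shown for systolic pressure.

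- The pressure limits in Protocol 5.1 apply at screening (day -14), whereas the model's baseline is Visit 3 (day 0), so neither modelled visit is truncated directly. A simulation of that window gave k = 1.00-1.06, which the formula turns into a type I error of 5.0-5.7%. It assumed systolic mean 130-140 and SD 12-18, diastolic mean 78 and SD 10, correlation 0.6 between the two, and screening correlations of 0.6-0.7 with day 0 and 0.4-0.6 with week 12.
- Protocol 5.3 expects similar pressure reductions with and without diabetes. If the drug affects no one's pressure, varying response cannot inflate type I error.
- SDs of 12 rising to 14 or 15, with correlation 0.4-0.6, imply a change SD of 11.8-15.0 mmHg. The plan assumes 8, and the pilot gave 10 (Protocol 5.3) or 10.8 (Protocol 2.5).

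All of this stands, and it limits what can be said about the primary test. It also stands that the SAP does not exclude visit-specific residual variances; it is silent, and compound symmetry is the ordinary reading. The missing degrees-of-freedom method is a separate, smaller matter: with equal variances, a z reference gives about 5.6-5.9%.

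The planned residual plots do not answer the point. No action is tied to them, and choosing a covariance after seeing the data would be data-driven. The SAP also invokes Welch-Satterthwaite for estimated plasma volume, so unequal variance was considered there but not for model 1.1.

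**Conclusion.** The concern holds, conditionally, for every outcome analysed with model 1.1. On the ordinary reading, the standard error is wrong by the factor sqrt((1 + k^2)/(2k^2)) whenever k differs from 1. The direction depends on whether spread grows or shrinks.

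A reader might infer that the primary systolic test is known to be anti-conservative. The documents do not support that: they give no visit-specific SDs, so neither the direction nor the size is established, and k below 1 makes the test conservative. A reader might also infer that every analysis is affected, but estimated plasma volume, analyses 3.2-3.7 and the safety counts use other methods. The sample size of 48 evaluable participants is not affected.

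The case is strongest for outcomes whose spread may rise sharply on drug. Urine glucose is the clearest example, but it is exploratory and its SDs here are assumed. The figures rest on a homoscedastic residual, complete normal data and 24 per arm. This is a worthwhile, inexpensive improvement rather than a demonstrated failure of the primary analysis.

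**What to change.** Keep the mean model in SAP 1.1 (visit and treatment-by-visit, common baseline). Replace the random intercept with an unstructured 2x2 within-participant covariance, fitted by REML with Kenward-Roger degrees of freedom, for all outcomes that use this model. Baseline-adjusted ANCOVA is equivalent with complete data; the mixed model also keeps participants who have only one of the two visits.

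The small-sample method should be named. The unstructured fit with a simple t reference rejected 4.6-6.5% in simulations of 3,000 trials per setting (Monte Carlo standard error about 0.4 points). The Kenward-Roger version was not itself simulated. A covariance common to both arms is adequate under 1:1 allocation even if spread rises in one arm only, as the 5.3% result above shows.

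The cost is a sentence in the SAP, three covariance parameters per model instead of two, and a slight loss of precision if the variances are in fact equal. Sample size and trial conduct do not change.
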